 - Patient Assessment of Upper Gastrointestinal Symptom Severity Index (PAGI-SYM) and the Gastrointestinal Symptom Rating Scale (GSRS).
 - Depression and anxiety using the Beck Depression Inventory and State-Trait Anxiety Scores.
 - Frequency of migraines and headaches (since many patients with gastroparesis have concomitant migraine) defined as, 'migraine day'= a migraine headache occurring in a 24-hour period, and a 'headache day'= any headache occurring in a single calendar day.
 - Autonomic symptoms as determined by the COMPASS-31 score.
- **3. Background** (briefly describe pre-clinical and clinical data, current experience with procedures, drug or device, and any other relevant information to justify the research)

Chronic nausea and vomiting are the clinical hallmarks of gastroparesis and Chronic Unexplained Nausea and Vomiting or CUNV (very similar to Functional Dyspepsia of the postprandial subtype, FD-PPS, by Rome criteria) or related disorders and in most cases, are constant and daily symptoms. However, in addition, the majority of these patients also experience periodic exacerbations of these symptoms either on a daily basis or several times in a week. These exacerbations require them to use "rescue" medications such as 5-HT3 antagonists (e.g. ondansetron) or D2 receptor antagonists (e.g. Promethazine). These are only partially effective at best and often associated with adverse effects. Our hypothesis is that nVNS may provide a more effective and safer alternative to the use of traditional rescue medications. We therefore believe that while nVNS may not necessarily be a stand-alone treatment for gastroparesis, it has the potential for meeting a large unmet "niche" need in this condition.

4. Study Procedures

Patients who appear to be eligible after chart review and completion of standard of care tests and procedures for gastroparesis, CUNV or related disorders will be invited to undergo screening for study. Patients considered by the clinical center investigator as likely to be eligible for participation in the trial may be consented, registered and screened at a visit that is part of the ongoing clinical care of the patient.

After informed consent is obtained, patients will fill out a validated symptom-based questionnaires and assessment daily.

Visit schedule

- At least 2 weeks of pre-treatment observation (screening).
- 8 weeks of treatment
- 2 weeks of post-treatment observation.
- Length of recruitment: 9 months

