As part of the screening process for the trial, the patient must have a diagnosis of gastroparesis or CUNV with delayed gastric emptying documented by gastric emptying scintigraphy (4-hour emptying after a low-fat meal with any combination of 2- and 4-hour retention of >60% and 10% respectively) and ongoing symptoms such as: nausea, vomiting, abdominal pain, etc. for at least 3 months without any other obvious cause. Patients must also have a normal upper endoscopy or standard radiography, to rule out other potential causes of symptoms such as mechanical obstruction, inflammatory or other structural lesions of the GI tract or non-gastrointestinal causes.

Recording of screening data on trial forms may not start until the patient has signed the informed consent form (ICF). Screening and baseline data collection procedures will include questionnaires, urine pregnancy test, 12 lead EKG, and review of the patient's medical chart.

All participants who sign the ICF will be registered in the trial database. Each participant who starts screening will be accounted for at the end of the screening, as either success or a screening failure. Screening failure is defined as a participant who signed the consent form and was registered in the trial data system, but is found to be ineligible prior to start of treatment. Screening failures include patients who meet medical eligibility criteria but change their mind and do not consent to participate in the trial. The reason for screening failure will be recorded and keyed into the database.

Screening visit:

The patient will undergo a medical history to identify other illness and contraindications for participations such as use of narcotics for more than 3 days per week, previous surgery of the upper gastrointestinal tract, history of prolonged QT interval or clinical significant arrhythmia, etc.

In addition, the patient will be provided with the questionnaires and will be administered on a daily basis for up two weeks before treatment with following questionnaires (delivered electronically):

- Gastroparesis Cardinal Symptom Index Daily Diary (GCSI-DD)

- Rescue medication uses daily diary- number of pills and type. Rescue medications that will be allowed for this trial are ondansetron, promethazine and prochlorperazine.
- Migraine and headache daily diary
- Gastrointestinal Symptom Rating Scale (GSRS)
- Patient Assessment of Upper Gastrointestinal Symptom Severity Index (PAGI-SYM)
- Beck Depression Inventory (BDI-II)

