The questionnaires will also be filled out during the treatment and during the 2 weeks after nVNS treatment has been completed. All questionnaires are short and easy to fill out with multiple-choice type responses. Adverse events (AEs) will also diarized.

All participants who sign the ICF will be registered in the trial database. Each participant who starts screening must be accounted for at the end of the screening, as either a screening success or a screening failure. A screening failure is defined and a participant who signed the consent form and was registered in the nVNS trial data system, but is found to be ineligible prior to start of treatment; screening failures include patients who meet medical eligibility criteria but change their mind and do not consent to participate in the trial. The reason for screening failure will be recorded and keyed into the trial database.

5. Inclusion/Exclusion Criteria

Inclusion criteria

- Age 15 years or older at registration.
- Diagnosis of gastroparesis as documented by gastric emptying scintigraphy (4-hour emptying after a low-fat meal with any combination of 2- and 4-hour retention of >60% and 10%, respectively), or Chronic Unexplained Nausea and Vomiting (CUNV).
- Ongoing symptoms (i.e. Nausea and vomiting, bloating, and abdominal pain) with a nausea score of 3 or more on the PAGI-SYM scale at baseline (moderate to severe nausea).
- Exclusion of other causes of symptoms such as mechanical gastrointestinal obstruction, uncontrolled esophagitis, peptic ulcer disease, etc. By standard radiographic or endoscopic tests.
- Use of the following medications on an as-needed basis: ondansetron, promethazine or prochlorperazine but no more than four times a day.

Exclusion criteria

- Another active disorder, which could explain symptoms in the opinion of the investigator.
- Age < than 15 years.
- Pregnancy or nursing.
- A previous surgery of the upper gastrointestinal tract, including vagotomy.
- Use of narcotics more than 3 days per week.
- History of prolonged QT interval or a history of clinically significant arrhythmia.
- Abnormal baseline ECG (e.g. Second- and third-degree heart block, atrial fibrillation, atrial flutter, recent history of ventricular tachycardia or ventricular fibrillation, or clinically significant premature ventricular contraction).
- Previous bilateral or right cervical vagotomy.
- Uncontrolled high blood pressure.

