- Currently implanted with an electrical and/or neurostimulator device, including but not limited to cardiac pacemaker or defibrillator, vagal neurostimulator, deep brain stimulator, spinal stimulator, bone growth stimulator, or cochlear implant.
- History of carotid endarterectomy or vascular neck surgery on the right side.
- Implanted with metal cervical spine hardware or has a metallic implant near the gammaCore stimulation site.
- Any other condition, which in the opinion of the investigator would impede compliance or hinder the completion of the study.
- Failure to give informed consent.

6. **Drugs/ Substances/ Devices**

gammaCore Sapphire (nVNS) ²³⁻²⁵

Description:

nVNS is a multi-use, hand-held, rechargeable, portable device consisting of a rechargeable battery, signal-generating and -amplifying electronics, and a control button for the patient to control the signal amplitude. The device provides visible (display) and audible (beep) feedback on the device and stimulation status. A pair of stainless steel surfaces, which are the skin contact surfaces ("stimulation surfaces"), allow the delivery of a proprietary electrical signal. The patient applies electroCore-approved gel to the stimulation surfaces to maintain an uninterrupted conductive path from the stimulation surfaces to the skin on the neck. Tubes of electroCore-approved gel are provided with each unit and refill kit for this purpose. The stimulation surfaces are capped when not in use.

7. Study Statistics

Data analysis will be performed at Mayo Clinic Scottsdale, Arizona by [name], ([contact]). This site will no recruit participants.

Johns Hopkins will serve as coordinating center, responsible for overall data management, monitoring and communication among both sites, and general oversight of the conduct of this protocol.

Outcome measures

Primary: The primary outcome measure is the average daily use of rescue medications for exacerbation of nausea/vomiting.

Sample size justification

- Primary endpoint: Improvement in nausea control, as defined by a 50% reduction n the number of weekly doses of rescue medications, compared with baseline.

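### Entry caps as-needed rescue use but sets no minimum, so very low users can be enrolled; for them the 50% responder endpoint is undefined or strongly affected by chance

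*Combined protocol and SAP*

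**What the plan says.** The only entry rule on rescue medication is in section 5, Inclusion criteria: "Use of the following medications on an as-needed basis: ondansetron, promethazine or prochlorperazine but no more than four times a day". The other inclusion and exclusion criteria and the screening text in section 4 give no minimum number of doses or days of use. A rescue diary is kept during screening, but no eligibility threshold is tied to it. A separate criterion asks for ongoing symptoms "with a nausea score of 3 or more on the PAGI-SYM scale at baseline (moderate to severe nausea"), which is a severity score and not a count of doses.

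Section 7 gives two versions of the primary measure. Outcome measures says: "The primary outcome measure is the average daily use of rescue medications for exacerbation of nausea/vomiting". Sample size justification says: "Improvement in nausea control, as defined by a 50% reduction n the number of weekly doses of rescue medications, compared with baseline". Neither states how a zero baseline is handled or which treatment weeks are compared with baseline.

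On timing, the visit schedule in section 4 has a pre-treatment period of two weeks or longer. The screening text says the questionnaires "will be administered on a daily basis for up two weeks before treatment". Treatment is "8 weeks of treatment", four on each side of the neck. Section 3 says that most of these patients "experience periodic exacerbations of these symptoms either on a daily basis or several times in a week", and that these episodes lead to rescue use.

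**The concern.** A percentage reduction from a patient's own baseline needs a baseline large enough to fall from. The entry rule does not secure that. A patient with constant moderate nausea who seldom takes an antiemetic meets both the nausea criterion and the as-needed criterion. Section 3 itself separates constant daily symptoms from the exacerbations that call for rescue medication, so the nausea score cannot stand in for a floor.

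If such a patient takes no dose in the run-in, the 50% endpoint cannot be calculated. If the patient takes one or two, ordinary variation can decide the result. Average daily use can still be calculated at zero, but that patient cannot improve on it. Because section 4 has the device used when a rescue dose would otherwise be taken, rare users also say little about the principal objective. Every group is stimulated, so no arm shows how often response occurs without the device.

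**Working it through.** **The plan's own figure.** Section 7 assumes 4/15, 11/15 and 7/15 responders (27%, 73%, 47%) and states a type I error below 0.05. It names no test. A Pearson chi-square on the 3 × 2 table gives 6.58 on 2 df, p = 0.037, and the exact test gives p = 0.046. The figure reproduces, as a p-value for assumed counts. It contains no allowance for chance response or for unclassifiable patients.

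**Inputs from the documents.** The baseline is about 2 weeks and treatment lasts 8 weeks. The comparison window is not named, so w = 8 and w = 4 weeks are both used. Response is taken as a weekly rate at or below half the baseline weekly rate.

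**Assumptions not in the documents.** There is no device effect, each patient has a constant true rate of λ doses a week, and dose counts are Poisson. A sensitivity run uses negative binomial counts with variance twice the mean.

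**Formulas.** Baseline count B ~ Poisson(2λ) and treatment count T ~ Poisson(wλ).
- Zero baseline: P(B = 0) = exp(−2λ).
- Response: T/w ≤ 0.5 × B/2, that is T ≤ wB/4. This means T ≤ 2B for 8 weeks and T ≤ B for 4 weeks.
- Chance response among classifiable patients: Σ over b ≥ 1 of P(B = b) × P(T ≤ wb/4), divided by 1 − P(B = 0).

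**Example, λ = 1, 8 weeks.** P(B = 0) = exp(−2) = 0.135. The terms for b = 1 to 8 are 0.0037, 0.0270, 0.0565, 0.0535, 0.0294, 0.0113, 0.0034 and 0.0009. With the small remainder the sum is 0.186, and 0.186 / 0.865 = 0.215.

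| Doses/week | Zero baseline, Poisson | Chance response among the rest, 8 wk / 4 wk | Zero baseline, variance 2 × mean | Chance response among the rest, 8 wk / 4 wk |
|---|---|---|---|---|
| 0.5 | 36.8% | 43.7% / 54.5% | 50.0% | 55.4% / 63.9% |
| 1 | 13.5% | 21.5% / 30.9% | 25.0% | 31.9% / 41.8% |
| 2 | 1.8% | 9.5% / 15.6% | 6.3% | 17.5% / 24.5% |
| 3 | 0.2% | 5.0% / 9.5% | 1.6% | 11.9% / 17.5% |
| 7 | <0.1% | 0.5% / 1.7% | <0.1% | 3.6% / 6.6% |

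A shorter window is worse. With 2 treatment weeks and Poisson counts, chance response is 37% at 1 a week, 16% at 3 a week and 5% at 7 a week.

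**Whole group.** Count zero-baseline patients as non-responders. Over 8 weeks with Poisson counts, chance response is then 27.6% of all patients at 0.5 a week (0.437 × 0.632) and 18.6% at 1 a week (0.215 × 0.865). For an illustrative mix of 20% at 0.5 a week and 80% at 7 a week, the group rate is 0.2 × 27.6% + 0.8 × 0.5% = 6%.

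**The case against.** The criterion does require as-needed use, so a patient who never takes these drugs fails it. Only a user who happens to take few or none in the run-in gets through, and no document says how many there would be. At the frequencies section 3 describes, the problem is modest to small. That limits the size of the point but does not supply a floor, because section 3 describes the majority and is not an entry rule.

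A reader might infer that low users will be enrolled in numbers and that the endpoint is largely chance for the trial as a whole. The documents do not support that. Chance dominates only at about 0.5 doses a week or less, and the mix of patients is unknown.

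A reader might also set the chance rates against the lowest planned success rate, 4/15 = 27%, and conclude that no effect is needed to reach it. That compares a rate among low users with a rate for a whole group. Over 8 weeks under Poisson counts, nearly everyone in a group would have to be at about 0.5 a week; the illustrative mix gives about 6%. A shorter window or extra variation raises these figures, but the mix remains unknown.

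Nor does chance response simply count as device effect. The sample-size argument compares three stimulated groups, and chance response common to all three dilutes that contrast without favouring a side. It inflates only the before-after reading.

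Finally, the undefined case belongs to the 50% definition, not to average daily use. That stands, and the two definitions in section 7 need reconciling.

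**Conclusion.** The gap is real and worth closing. As written, the plan can enrol patients whom the 50% endpoint cannot classify, or whom it classifies with a strong element of chance, at about 1 dose a week or less. With no effect and Poisson counts, 14% at 1 a week have a zero baseline and 22% to 31% of the rest respond by chance; at 0.5 a week it is 37% and 44% to 55%. At 3 a week chance response is 5% to about 10% (12% to 18% if variance is twice the mean). At daily use it is about 0.5% to 2% under Poisson counts for windows of 4 to 8 weeks.

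These sizes rest on an assumed count model, a constant rate and a comparison window that the plan does not name. The missing floor and the missing zero-baseline rule can be read directly from the text; the effect on this pilot cannot be. With 15 patients per group, each misclassified patient moves a group's rate by 1/15, or 6.7 percentage points.

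**What to change.** Add to section 5 a minimum as-needed rescue use at entry that matches the frequency described in section 3. The sponsor should choose and justify the value; an average of 3 times a week is one example, and the table shows what different rates leave to chance. Take it from the screening history and not from the run-in diary, so that the selection measure is not also the baseline. This reduces regression to the mean but does not remove it, since a recalled history can also catch a bad spell.

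Add to section 7 that an enrolled patient with no rescue dose in the baseline counts as a non-responder on the 50% endpoint, and name the treatment weeks compared with baseline. The zero-baseline rule alone would settle the undefined case but would leave the chance response among low users.

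The cost is a few lines of text, somewhat slower recruitment at one site over 9 months (the documents give no figure to size this), and results that apply only to regular rescue users.

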- State- Trait Anxiety Inventory (STAI)
- Average weekly frequency of migraine headaches for the last 4 week period
- COMPASS-31 score.

Anthropomorphic assessments (body weight, body height, body mass index [BMI]. Pregnancy test results that need to be recorded from chart review or obtained as part of the screening and EKG to rule out any abnormal baseline electrocardiogram such as second and third degree heart block, atrial fibrillation, atrial flutter, recent history of ventricular tachycardia or ventricular fibrillation, or clinically significant premature ventricular contraction, history of prolonged QT interval or a history of clinically significant arrhythmia.

Data will be captured on REDCAP and stored on the secure Hopkins server for this purpose.

2. Treatment Start Visit

At this visit, the patient will receive the gammaCore (nVNS) device and a video instruction will be use to explain how to properly handle the device. Treatment can only start after eligibility has been fully checked and all data collected at screening have been keyed into the trial database. Women of childbearing potential must have a negative urine pregnancy test.

After eligibility is confirmed with the clinical center staff the treatment can begin. The date of starting treatment is the start (ZERO) time for the timing of follow-up visits.

Frequency and duration of nVNS treatment.

The treatment will be self-administered using nVNS and will be applied for 8 weeks; 4 weeks will be used on one side of the neck and other 4 weeks in the contralateral side. A member of the study will provide the proper training on the correct use of nVNS. The patient will be instructed to use the nVNS in place of the rescue medications. When the nauseas gets bad enough that they feel to use a rescue medication they will first use the device on one side of the neck for two 2minute stimulations and wait fifteen minutes to check if the stimulation works. If this does not help either, they will stimulate with an additional 2 stimulations and wait for another fifteen minutes. If there is no improvement rescue medication will be used. nVNS can be used up to, but no more than, 8 times a day.

3. Follow-up Visits

Patients will return for follow-up visits at 4 and 10 weeks after treatment initiation. The specific

procedures to be completed at each of the follow-up visits are:

- Week 4 visit: The following questionnaires should be completed and collected:

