- Total of 45 patients. This is a pilot study to assess the strength of the signal (improvement) with peripheral VNS for nausea. Since there is evidence that the left and right vagus may have different pathways within the CNS, with the left side being dominant in innervation of center involved in food aversion and nausea (Cell 175, 665–678, 2018), we are proposing to study three groups as follows
 - Group 1; Start with left sided stimulation 15 patients
 - Group 2. Start with right sided stimulation 15 patients
 - Group 3. Both sided stimulation 15 patients
- Our assumptions are as follows, in terms of the number of patients improving in each group

Group 1: 4/15 Group 2: 11/15 Group 3: 7/15

If these assumptions are true, the type I error will be < 0.05

8. Risks³²⁻³⁴

The adverse reactions observed in nVNS studies include:

- i. Shortness of breath (dyspnea), hoarseness, or change in voice during treatment.
- ii. Muscle twitching, discomfort, or pain during stimulation.
- iii. Change in taste (dysgeusia).

These first three reactions resolved after treatment was completed.

- iv. Local skin irritation/inflammation.
- v. Any progression of headache symptoms.

Adverse reactions not seen in the studies, but associated with implanted vagal nerve stimulation devices include:

- vi. Tingling, pricking, or a feeling of "pins and needles" on the skin where the device is applied (paresthesia or dysaesthesia) lasting beyond the treatment period.
- vii. Fainting (syncope), light-headedness, and/or dizziness.
- viii. Sweating.
- ix. Fatigue, depressed mood.
- x. Tinnitus.
- xi. Diarrhea.
- xii. Abnormal heart rhythm.

Adverse events will be evaluated in every follow-up visit. A form of Adverse Event will be completed if the candidate complains of any symptoms, sign, abnormal assessment or any combination of these. An adverse event can be expected side effect that is of a serious nature, or an unexpected side effect/event regardless of severity.

This study will monitor and report adverse events to ensure patient safety to IRB and FDA. Signs and symptoms associated with the adverse event will be graded as to severity by the clinical site staff as mild, moderate, or sever using Version 5.0 of the National Cancer Institute's Common Terminology Criteria for Adverse Events (CTCAE).

9. Benefits

Description of the probable benefits for the participant and for society.

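### Two neck-surgery exclusions are limited to the right (or both sides) although the left side is also stimulated, and the minimum age is 18 in section 4 but 15 in section 5

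*Combined protocol and SAP*

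**What the plan says.** **Neck history.** The exclusion list in section 5 contains "Previous bilateral or right cervical vagotomy" and "History of carotid endarterectomy or vascular neck surgery on the right side". It also contains "A previous surgery of the upper gastrointestinal tract, including vagotomy", which has no side limit but concerns gastrointestinal surgery.

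**Stimulation.** Section 4, under frequency and duration of treatment, states that "4 weeks will be used on one side of the neck and other 4 weeks in the contralateral side", and that "nVNS can be used up to, but no more than, 8 times a day". Section 7, under sample size justification, describes three groups of 15. They include "Group 1; Start with left sided stimulation 15 patients" and "Group 3. Both sided stimulation 15 patients"; the remaining group starts on the right.

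**Age.** The section 5 inclusion list reads "Age 15 years or older at registration", and its exclusion list repeats the limit by excluding anyone under 15. The screening text in section 4 gives the limit as 18. The consent procedure in section 4 describes signature by the participant and by the study coordinator. It mentions neither parental permission nor assent.

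**The concern.** The plan treats earlier surgery on the vagus or the neck vessels as a reason not to take part when it was on the right. The background in section 1 explains that the device acts on vagal fibres within the carotid sheath, so the relevant history is surgery on whichever side is stimulated. The wording would suit a trial that stimulates only the right side, and this trial does not. No reason is given for accepting the same history on the left. At stake is the safety of the few individuals concerned, who would be told to stimulate an operated side.

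The age conflict is a separate matter. A patient aged 15 to 17 is eligible under one section and ineligible under the other, so enrolling that patient breaks section 4 and refusing breaks section 5. If such a patient is enrolled, the consent steps as written do not fit a minor.

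**Working it through.** The plan states no figure on this point, so the check is a comparison of texts followed by a rough sizing.

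**1. Who stimulates the left side?**
- Section 4: every patient uses both sides, 4 weeks each. That is all 45 patients in section 7, or all of the approximately 30 in section 4.
- Section 7, counting only the left-start and both-sides groups: 15 + 15 = 30 of 45. The right-start group reaches the left side when it switches.

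**2. Which histories are excluded by name?**

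| History | Right | Left only |
|---|---|---|
| Cervical vagotomy | excluded | not named |
| Vascular neck surgery other than endarterectomy | excluded | not named |
| Carotid endarterectomy | excluded | depends on reading |

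The last row turns on grammar. If the side limit governs both procedures, left endarterectomy is allowed. If it governs only vascular neck surgery, endarterectomy on either side is already excluded.

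**3. Does another criterion close the gap?**
- The upper gastrointestinal surgery exclusion names vagotomy as an example of such surgery. If it covered every vagotomy, the separate cervical line would be redundant. It does not reach vascular neck surgery.
- The implanted-stimulator and metal-implant exclusions concern hardware, not surgical history.
- The investigator-discretion exclusion is limited to compliance and completion.
- The screening history in section 4 is open-ended but does not name neck surgery.

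**4. Size.** The documents give no prevalence. Assume that a proportion p of otherwise eligible patients, between 0.001 and 0.01, has a left-only history. The expected number is N × p, and the chance of at least one is 1 − (1 − p)^N.

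| N | p | Expected number | Chance of at least one |
|---|---|---|---|
| 45 | 0.001 | 0.045 | 1 − 0.999^45 = 0.044 |
| 45 | 0.01 | 0.45 | 1 − 0.99^45 = 0.364 |
| 30 | 0.001 | 0.03 | 1 − 0.999^30 = 0.030 |
| 30 | 0.01 | 0.30 | 1 − 0.99^30 = 0.260 |

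The ceiling on exposure of the affected side for one patient under the section 4 schedule is 8 uses a day × 28 days = 224 uses.

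**5. Age.** Section 4 requires at least 18; section 5 requires at least 15. The two rules disagree for ages 15, 16 and 17 and agree at every other age. The documents do not allow an estimate of how many such patients would present.

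**The case against.** The strongest reply is that an investigator could still keep these patients out. Section 5 also excludes another active disorder that could explain the symptoms, and section 4 requires that symptoms have no other obvious cause. The introduction says that vagal injury can slow gastric emptying, so a left cervical vagotomy might be treated as the explanation. A patient who could not use one side might also be judged unable to complete the study. These routes exist, but each depends on one investigator's reading, and it is arguable whether an old nerve section counts as an active disorder. None of them names left vascular neck surgery.

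A second reply is that the plan documents no hazard: section 8 lists no risk tied to earlier neck surgery, and for vagotomy a loss of effect is as plausible as harm. That is fair. The inference of risk comes from the plan's own decision to exclude the right-sided histories.

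Third, the prevalence range has no anchor in the documents, and 224 uses is a maximum. Use is as needed, and rescue medication at entry is limited to four times a day. If each round of stimulation counts as one use, 8 a day means four episodes, each needing both rounds, every day for 28 days. Typical exposure would be lower. This also stands.

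On age, section 5 is the formal list and gives 15 twice, so staff would probably follow it. That makes the consent gap more pressing, because following section 5 is what admits minors. The consent form pages were not available, so the gap is claimed only for the section 4 procedure.

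**Conclusion.** Both points hold. As written, no criterion names left-only cervical vagotomy or left vascular neck surgery, although the left side is stimulated in all patients under section 4. Left endarterectomy is uncovered on one of two readings. The effect is small in numbers: at most 0.45 expected patients of 45 if prevalence is no higher than the assumed 1%. It is a matter of individual safety, and no effect on the trial's results is claimed. The age limits contradict each other for ages 15 to 17; this needs no assumption. Both should be corrected, and confidence in the reading is high.

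**What to change.** Replace the two exclusion lines in section 5 with:
- *Any previous cervical vagotomy (left, right or bilateral).*
- *History of carotid endarterectomy or vascular neck surgery on either side.*

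State one age limit in sections 4 and 5. If 18 is chosen, change both age lines in section 5. If 15 is kept, change the section 4 sentence and add parental permission and participant assent to the consent procedure there.

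The cost is a wording amendment. A medical history is already taken at screening, so the side rule adds no procedure, and very few patients would be lost to it.

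### Two unlinked primaries with no treatment window: the choice of weeks decides whether the left-versus-right contrast that sizes the trial is present, absent or reversed

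*Combined protocol and SAP*

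**What the plan says.** Section 7, under Outcome measures, states: "The primary outcome measure is the average daily use of rescue medications for exacerbation of nausea/vomiting". A few lines later, under Sample size justification, the primary endpoint is "Improvement in nausea control, as defined by a 50% reduction n the number of weekly doses of rescue medications, compared with baseline". The first is a mean and the second is a yes/no result for each patient. No sentence connects them, and neither names treatment weeks.

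The sizing then sets out three groups of 15. Two are defined by where they begin: "Group 1; Start with left sided stimulation 15 patients" and "Group 2. Start with right sided stimulation 15 patients". The third receives stimulation on both sides. The stated reason for the groups is that the left and right vagus may act differently. The assumed numbers improving are "Group 1: 4/15 Group 2: 11/15 Group 3: 7/15", said to give a type I error below 0.05.

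Section 4 (Frequency and duration of nVNS treatment) sets 8 weeks of treatment, of which "4 weeks will be used on one side of the neck and other 4 weeks in the contralateral side". The schedule table collects the rescue diary at treatment initiation and at weeks 4, 8 and 10.

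On the unit of measurement, the screening list asks for "Rescue medication uses daily diary- number of pills and type". Specific Tests and Questionnaires adds dosage and frequency. Three drugs are allowed, and no rule turns these entries into a number of doses.

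**The concern.** Three choices are left open, and each can change the result.

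- **Which primary.** Only the responder endpoint is sized, but average daily use is what the plan calls the primary outcome measure. The two can point in different directions on the same data.
- **Which weeks.** Starting side separates Groups 1 and 2 only until the switch. A window that spans the switch mixes the two sides within each patient.
- **Which unit.** Pills and dosing occasions can classify the same patient differently.

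If these are settled after the data are seen, the team could report several answers from one trial. If they are settled by defaulting to the whole treatment period, the comparison that justified the sample size has little chance of showing a side difference that exists.

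**Working it through.** **1. The plan's own figure.** Inputs are 4, 11 and 7 responders out of 15 (Section 7). The mean count is 22/3 = 7.33. For equal groups, chi-square = (sum of squared deviations) × (1/7.33 + 1/7.67) = 24.67 × 0.2668 = 6.58 on 2 df, so p = 0.037. The exact three-group p-value is 0.046. The stated value below 0.05 therefore reproduces, but it is the p-value of the assumed table and not a type I error.

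**2. What drives it.** Pairwise two-sided Fisher tests:

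| Comparison | p |
|---|---|
| Start left v start right (4/15 v 11/15) | 0.027 |
| Start left v both (4/15 v 7/15) | 0.45 |
| Start right v both (11/15 v 7/15) | 0.26 |

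The sized result rests on left v right.

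**3. Exposure by window.**

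| Window | Group 1 | Group 2 | Expected response if only side matters |
|---|---|---|---|
| Weeks 1-4 | left | right | 27% v 73% |
| Weeks 5-8 | right | left | 73% v 27% |
| Weeks 1-8 | 4 weeks of each | 4 weeks of each | equal |

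To put a level on the last row, assume that each patient's ratio of treatment to baseline doses is log-normal on each side, with 4/15 at or below 0.5 on the left and 11/15 on the right. The log-scale means are then ln 0.5 ± 0.623 × SD. The 8-week ratio is the average of the two side ratios, whichever comes first. With SD from 0.3 to 1.0 and between-side correlation from 0 to 1, the 8-week response is 34% (SD 1.0, correlation 0) to 48% (SD 0.3, correlation 1), the same in both groups. The SD and correlation are assumptions, because the documents give neither.

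**4. Power, three-group chi-square, 15 per group, by exact enumeration.**

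| Rates (Groups 1, 2, 3) | Chance of p < 0.05 |
|---|---|
| 4/15, 11/15, 7/15 | 66% |
| 34%, 34%, 7/15 | 11% |
| 40%, 40%, 7/15 | 6% |
| 48%, 48%, 7/15 | 5% |

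Group 3 is held at 7/15 because Section 4 gives no both-sided schedule from which to derive anything else.

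**5. If the mixing is incomplete.** Suppose carry-over or order effects let half the left-right gap survive over 8 weeks (38% v 62%). Two-group power is then 24% (Pearson) or 13% (Fisher), against 74% and 60% for the full gap.

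**6. The two primaries can disagree.** These cases are built to show it and are not forecasts.
- Eight of 15 patients go from 3.5 to 1.75 doses a week and seven stay at 28 (the Section 5 limit of four times a day, × 7). Responders: 8/15 = 53%. Total use goes from 8 × 3.5 + 7 × 28 = 224 to 210, a fall of 14/224 = 6%.
- Every patient falls by exactly 40%. Mean use falls 40% and nobody reaches 50%.

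**7. The unit.** A patient with seven dosing occasions a week who goes from two pills to one each time goes from 14 to 7 by pills (responder) and from 7 to 7 by occasions (non-responder).

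**The case against.** The strongest reply has three parts.

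First, a measure and an endpoint are not rivals. A 50% cut of a diary measure is ordinary, both come from the same rescue diary, and the disagreement cases above are chosen to disagree. This partly stands. A reader might infer that the two statements contradict each other outright, and the documents do not show that. They may be one outcome and its dichotomy. But the plan does not say so, calls both primary, and leaves the window and unit missing from each.

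Second, a reader might infer that the side switch has already destroyed the left-right comparison. The documents do not support that. Weeks 1-8 is one reading among several. Naming the groups by starting side and collecting the diary at week 4 both fit a comparison made before the switch. The zero difference is also exact only without carry-over, period or order effects. If such effects left a difference over 8 weeks, it would not cleanly estimate a side effect. A within-patient comparison of sides is possible, but none is described or sized.

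Third, this is an open-label pilot whose principal objective (Section 2) is whether rescue use falls, not which side is better. That stands, and it is a reason not to displace the before-after question. It does not excuse the gap, because Section 7 sizes the trial on the group comparison.

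**Conclusion.** The point holds as a failure to define the primary. Two primaries are named without a link, only one is sized, and neither has a window or a dose unit. The window matters most: weeks 1-4 keep the assumed 27% v 73% gap, weeks 5-8 reverse it, and weeks 1-8 give an expected difference of zero. Three-group power goes from about 66% at the assumed rates to about 5-11% over weeks 1-8.

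The zero difference assumes no carry-over, period or order effect. The 34-48% response level, and so the 5-11%, also assumes log-normal dose ratios and Group 3 at 7/15. The 66% takes the plan's response rates at face value and assumes 45 evaluable patients.

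This should be settled before any outcome data are examined.

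**What to change.** 1. Name one primary and state how the other relates to it. For example, keep the sized 50% responder endpoint for the group comparison and report average daily use as its continuous companion. The reverse is equally acceptable if the sizing is restated for average daily use.
2. Define the between-group comparison on weeks 1-4, before the side switch, against the screening-diary baseline.
3. Keep the Section 2 question (does rescue use fall?) as its own stated analysis with its own window, for example weeks 1-8 with all groups pooled.
4. Define one dose unit across the three drugs, for example dosing occasions, with pill count as a sensitivity analysis. Section 5 caps as-needed use but sets no minimum, so also state that patients with zero baseline use count as non-responders, and report their number.

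The cost is protocol and SAP wording, because the diary is already collected at initiation and week 4. The drawback is that the group comparison uses 28 rather than 56 diary days.

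Two related conflicts must be reconciled by the sponsor at the same time. Section 4 expects about 30 patients and Section 7 has 45. Section 7 has a both-sided Group 3, while Section 4 describes only one side followed by the other.
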